#### 8.4 Concomitant Medication

Participants are allowed to continue the use of concomitant medication, which will be recorded in the CRF. If concomitant treatment has to be changed during the study period, this must be reported on the CRF provided (trade name and/or generic name) and in the participant's medical records. Addition of any medication that will significantly influence weight and glucose levels, such as corticosteroids, during the period of the study, is reason for discontinuation of the participant in the study

#### 9. SAFETY REPORTING

#### 9.1 Definitions

#### 9.1.1 Adverse Event (AE)

An AE or adverse experience is:

Any untoward medical occurrence in a patient or clinical investigation participants, which does not necessarily have to have a causal relationship with this treatment.

An AE can therefore be any unfavourable and unintended sign (including an abnormal laboratory finding), symptom or disease temporally associated with the study, whether or not considered related to the study.

#### 9.1.2 Adverse Reaction (AR)

All untoward and unintended responses related to the study.

All cases judged by either the reporting medically qualified professional or the sponsor as having a reasonable suspected causal relationship to the study qualify as adverse reactions.

#### 9.1.3 Severe Adverse Events

To ensure no confusion or misunderstanding of the difference between the terms "serious" and "severe", which are not synonymous, the following note of clarification is provided:

The term "severe" is often used to describe the intensity (severity) of a specific event (as in mild, moderate, or severe myocardial infarction); the event itself, however, may be of relatively minor medical significance (such as severe headache). This is not the same as "serious," which is based on patient/event outcome or action criteria usually associated with events that pose a threat to a participant's life or functioning. Seriousness (not severity) serves as a guide for defining regulatory reporting obligations.

#### 9.1.4 Serious Adverse Event or Serious Adverse Reaction

A serious adverse event or reaction is any untoward medical occurrence that at any dose:

- Results in death,
- Is life-threatening,

NOTE: The term "life-threatening" in the definition of "serious" refers to an event in which the participant was at risk of death at the time of the event; it does not refer to an event which hypothetically might have caused death if it were more severe.

- Requires inpatient hospitalisation or prolongation of existing hospitalisation,
- Results in persistent or significant disability/incapacity, or
- Is a congenital anomaly/birth defect.
- Other important medical events\*

\*Other events that may not result in death, are not life threatening, or do not require hospitalisation, may be considered a serious adverse event when, based upon appropriate medical judgement, the event may jeopardise the patient and may require medical or surgical intervention to prevent one of the outcomes listed above.

#### 9.1.5 Expected Serious Adverse Events/Reactions

No serious adverse events/reactions are expected in this study. However, any Serious Adverse Events/Reactions other than death will only be reported to the Sponsor if it is deemed to be related to the study procedures. For example planned routine and elective surgery will not be reported to the sponsor.

#### 9.1.6 Suspected Unexpected Serious Adverse Reactions

A serious adverse reaction, the nature or severity of which is not consistent with the applicable product information

#### 9.2 Reporting Procedures for All Adverse Events

All AEs occurring during the study observed by the investigator or reported by the participant, whether or not attributed to study, will be recorded on the CRF.

The following information will be recorded: description, date of onset and end date, severity, assessment of relatedness to study, other suspect device and action taken. Follow-up information should be provided as necessary.

AEs considered related to the study as judged by a medically qualified investigator or the sponsor will be followed until resolution or the event is considered stable. All related AEs that result in a

Page 51 of 81

participant's withdrawal from the study or are present at the end of the study, should be followed up until a satisfactory resolution occurs.

It will be left to the investigator's clinical judgment whether or not an AE is of sufficient severity to require the participant's removal from treatment (see section 7.7). A participant may also voluntarily withdraw from treatment due to what he or she perceives as an intolerable AE. If either of these occurs, the participant must undergo an end of study assessment and be given appropriate care under medical supervision until symptoms cease or the condition becomes stable.

The severity of events will be assessed on the following scale: 1 = mild, 2 = moderate, 3 = severe. The relationship of AEs to the study will be assessed by a medically qualified investigator.

#### 9.3 Reporting Procedures for Serious Adverse Events

All SAEs, except those expected ones defined in section 9.1.5 that do not require immediate reporting (see 9.1.5), must be reported to the Sponsor within one working day of discovery or notification of the event. The Sponsor will perform an initial check of the information and ensure that it is reviewed at the next R&D Management meeting. All SAE information must be recorded on an SAE form and sent to the Sponsor using the appropriate reporting form and the contact details on there. Additional information received for a case (follow-up or corrections to the original case) needs to be detailed on a new SAE form which must be sent to the Sponsor using the appropriate reporting form and the contact details on there.

The Sponsor will report all SUSARs to the Research Ethics Committee concerned. Fatal or life-threatening SUSARs must be reported within 7 days and all other SUSARs within 15 days. The CI will inform all investigators concerned of relevant information about SUSARs that could adversely affect the safety of participants.

In addition to the expedited reporting above, the CI shall submit once a year throughout the study or on request an Annual Report to the Ethics Committee which lists all SAEs / SUSARs that have occurred during the preceding 12 months.

#### 9.4 Definitions of hypoglycaemia (HYPO)

A HYPO episode will be defined as treatment emergent if the onset of the episode is on or after the first day of randomised treatment and no later than 24h after completion of the second intervention

in the study. Hypoglycaemic events will be defined as nocturnal if the time onset is between 00:01 and 05:59 (both included).

A HYPO episode form and an Adverse Event (AE) form must be filled in for all HYPO episodes. HYPO episodes requiring the assistance of another person to actively administer carbohydrate, glucagon, or other resuscitative actions (i.e., 'severe HYPO episodes') will be qualified as an event of special interest and must be reported as an SAE. These will be checked for at each of the visits the participant attends as well as the safety calls conducted. Details of the episode(s) and resolution(s) will be documented.

# Definition of hypoglycaemia during daily life

All participants will be supplied with a glucose monitoring diary for recording symptoms suggestive of hypoglycaemia and a glucose meter for measurement and documentation of capillary blood glucose levels at the time of the HYPO symptoms, as well as documentation of treatment received. Capillary blood glucose will be measured in all participants when there is a suspicion of HYPO.

All blood glucose values <3.0mmol/L (55mg/dL), as well as values ≥3.0mmol/L (55mg/dL) when hypoglycaemic symptoms have occurred should be recorded by the participants in the diaries. Hypoglycaemic episodes must be transcribed into the CRF by the study team throughout the trial.

#### Hypoglycaemia classification during daily life

Severe hypoglycaemia: An episode requiring assistance of another person to actively administer carbohydrate, glucagon, or other resuscitative actions. This would be classed as a SAE.

Documented symptomatic hypoglycaemia: An episode during which typical symptoms of hypoglycaemia are accompanied by a measured blood glucose concentration <3.0mmol/L.

Asymptomatic hypoglycaemia: An episode not accompanied by typical symptoms of hypoglycaemia, but with a measured blood glucose concentration <3.0mmol/L.

Probable symptomatic hypoglycaemia: An episode during which symptoms of hypoglycaemia are not accompanied by a blood glucose determination (but that was presumably caused by a plasma glucose concentration <3.0mmol/L).

Relative hypoglycaemia: An episode during which the participant reports any of the typical symptoms of hypoglycaemia and interprets those as indicative of hypoglycaemia, but with a measured blood glucose concentration ≥3.0mmol/L.

#### Definition of hypoglycaemia during analysis of the blinded CGM (Dexcom G6)

An episode of hypoglycaemia on CGM will be defined as at least 2 sensor values <3.0mmol/L (54mg/dl) that were 15 or more minutes apart with no intervening values ≥3.0mmol/l. At least 2 sensor values ≥3.9mmol/l that were 15 or more minutes apart with no intervening values <3.9mmol/l will be required to define the end a hypoglycemic event.

Symptomatic hypoglycaemia during CGM will be defined as an episode of hypoglycaemia on CGM (defined as above) accompanied with typical symptoms of hypoglycaemia which have been documented at the glucose monitoring diary

Asymptomatic hypoglycaemia during CGM will be defined as an episode of hypoglycaemia on CGM (defined as above) not accompanied with typical symptoms of hypoglycaemia or without documentation of symptoms at that time at the glucose monitoring diary.

Probable symptomatic hypoglycaemia: An episode during which symptoms of hypoglycaemia are not accompanied by a interstitial glucose determination (but that was presumably caused by a plasma glucose concentration <3.0mmol/L).

Relative hypoglycaemia: An episode during which the participant reports any of the typical symptoms of hypoglycaemia and interprets those as indicative of hypoglycaemia, but with interstitial glucose levels  $\geq 3.0$  mmol/L.

#### Definition of hypoglycaemia during the mixed meal tolerance test (MMTT)

Asymptomatic hypoglycaemia during the MMTT will be defined as plasma glucose <3.0 mmol/l not accompanied with typical symptoms of hypoglycaemia.

Symptomatic hypoglycaemia during the MMTT will be defined as plasma glucose <3.0 mmol/l accompanied with typical symptoms of hypoglycaemia.

Relative hypoglycaemia during MMTT will be defined as an episode during which the participant reports any of the typical symptoms of hypoglycaemia and interprets, but plasma glucose levels are ≥3.0 mmol/L.

It is noted that decisions regarding treatment of hypoglycaemia during the MMTT will be made in accordance with venous blood glucose/capillary blood glucose values and symptoms of the patient (instead of plasma glucose levels which will be performed at the UHL lab). More specifically if the participant experiences symptoms suggestive of hypoglycaemia and venous blood glucose/capillary blood glucose levels are <3.0mmol/l, then the participant will receive treatment for HYPO in accordance with HYPO Guideline for Adults of the UHL and the blood collection for measurement of insulin, glucose and appetite biomarkers as well as the VAS score collection for hunger and satiety during the MMTT will be terminated. The participant will remain in sitting position after HYPO treatment until the expected time of completion of the experimental period. It is noted that it is not expected that patients will experience severe hypoglycaemia during the study as patients will be excluded at screening if they have an established diagnosis of PHH after bariatric surgery.

#### 10. RESPONSE TO THE COVID-19 GLOBAL PANDEMIC

Due to the current global pandemic we will not encourage participants to attend or take part if it poses a risk to them. We will encourage participants to attend visits by themselves to reduce people coming into the Leicester Diabetes Centre. Prior to each visit participants will also undergo a COVID-19 check which includes a temperature check and some questions and if participants are able to they must wear a face mask/covering when they attend their appointment as per NHS Trust Guidance. The risk of COVID-19 infection will be minimised by staff wearing PPE and following NHS Trust Guidance and having Study Risk Assessments in place to reduce risk of infection.

To ensure safety of participants and staff at Leicester Diabetes Centre, all clinical areas used for research visits will have Risk Assessments completed to ensure mitigations are in place where risks are identified - this will be carried out prior to starting any study visits. Study based Risk Assessments will be completed also and in agreement with sponsor, study team and NHS Host Organisation will also be put in place to ensure appropriate measures are in place to carry out study delivery in a safe manner. Visits 0, 1, 2 and 4 will take place as face to face visits due to the nature measurements and procedures required for this study. Visits 3 and 5 can be optional to attend where CGM device would not require re-insertion or to be removed by study team.

If the study team is required to visit GP Practice, community venues or any other organisation, they must adhere to COVID-19 National Government Guidance and any other measures in place within the individual organisation.

#### 11. STATISTICS

#### 11.1 Description of Statistical Methods

A CONSORT study flow diagram will detail the movement of participants throughout the BariEX study. Baseline descriptive characteristics will be summarised, with continuous variables expressed as mean values (and standard deviations) or median values (with lower and upper quartiles) where appropriate, and binary and categorical variables expressed as number (percentage). Where CGM data is missing from a given trial, the corresponding data will be excluded from the other trial during the same time period at the second treatment. Participants with less than 16-hours 48min CGM data available for analysis over the 24-hour period after the intervention will be excluded from the complete cases analysis. The primary outcome of the study will be the difference in the time spent in HYPO (defined as glucose levels <3.0 mmol/l as measured by CGM) between the AEX and control intervention during the first 24-h post-intervention.

For outcomes related to the standardized MMTT (secondary outcomes), data from blood samples collected pre-MMTT at lunchtime (exactly before MMTT consumption) and 15, 30, 60, 90, 120, 150 and 180 minutes after MMTT consumption (last mouthful of MMTT) will be used to calculate time-averaged AUC (Area Under the Curve), using the trapezium rule. In instances of symptomatic hypoglycaemia during the MMTT(where blood collection for glucose, insulin and appetite biomarkers as well as VAS scores for satiety and hunger will be terminated early), these participants will be excluded from the analysis of secondary outcomes related to the MMTT. Missing data on insulin, glucose, appetite biomarkers and VAS scores for satiety and hunger within a completed MMTT will be imputed using a linear regression method as previously reported (35, 36), provided baseline/pre meal value and ≥50% of data points within the MMTT are available. The primary and secondary outcomes will be analysed using GEE (Generalised Estimating Equations) with an exchangeable correlation matrix, taking into account repeated measures across conditions. Outcome distribution will be assessed, with Gamma models used for positively skewed data. Identity and log link functions will be explored with Gamma models, with an identity link preferred (to aid interpretation of results) unless log link provides a substantially superior model fit.

The primary and main secondary outcomes will be analysed using a complete case approach. A sensitivity analysis will also be conducted where individuals in whom rescue action for symptomatic hypoglycaemia during the first 24-h post-intervention was required will be excluded from the

analysis. A second sensitivity analysis will be performed using individuals with any CGM data (i.e. including those with CGM data available for analysis is <16hours 48mins for the first 24 hours post-intervention). A value of P<0.05 will be considered statistically significant for all analyses. Statistical analyses will be carried out using commercially available statistical programmes.

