## 4.2 Secondary Objectives

- 1) To assess the differences in CGM metrics (32) between the AEX and control (prolonged sitting) for the 24-h period after completion of the intervention [including CGM mean glucose concentrations, glucose variability, the time in hyperglycaemia and time in range (see section 5.2 for definitions of hyperglycaemia and time in range)].
- 2) To assess the difference between AEX and control condition in mean nadir interstitial glucose levels, the risk of hypoglycaemia (assessed through the low blood glucose index), the risk of hyperglycaemia (assessed through the high blood glucose index), the total number (symptomatic and asymptomatic) of HYPO episodes (defined as glucose levels <3.0mmol/l) during daily life and the number of symptomatic HYPO episodes requiring treatment for the 24-h period following intervention.
- 3) To assess the change in the nadir, peak and postprandial blood glucose levels [assessed by the area under the curve (AUC)] and the peak and postprandial (assessed by the AUC) insulin levels after a standardised lunch.

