## Secondary outcomes:

- 1. Difference in Area Under the Curve (AUC)(0-180), pre-meal, peak and nadir glucose levels after mixed meal tolerance test (3-h MMTT) between the two interventions (AEX vs control) after bariatric surgery (RYGB and SG).
- 2. Difference in  $AUC_{(0-180)}$  insulin, pre-meal and peak insulin levels during the 3-h MMTT between the two interventions (AEX vs control) after bariatric surgery (RYGB and SG).
- 3. Difference in the ratio  $AUC_{(0-180)}$  insulin/ $AUC_{(0-180)}$  glucose during the 3-h MMTT between the two interventions (AEX vs control) after bariatric surgery (RYGB and SG).
- 4. Difference in the ratio  $AUC_{(0-30)}$  insulin/ $AUC_{(0-30)}$  glucose during the 3-h MMTT between the two interventions (AEX vs control) after bariatric surgery (RYGB and SG).
- 5. Difference in the ratio  $AUC_{(60-180)}$  insulin/ $AUC_{(60-180)}$  glucose during the 3-h MMTT between the two interventions (AEX vs control) after bariatric surgery (RYGB and SG).
- 6. Difference in the ratio of maximum/minimum plasma glucose during the 3-h MMTT between the two interventions (AEX vs control) after bariatric surgery (RYGB and SG).
- 7. Difference at the number of mixed meal tests required to be stopped due to symptomatic HYPO with blood glucose/capillary glucose levels <3.0 mmol/l during the 3-h MMTT between the two interventions (AEX vs control) after bariatric surgery (RYGB and SG).
- 8. Difference in %time in interstitial glucose levels <3.9 mmol/l in CGM between the two interventions (AEX vs control) after bariatric surgery (RYGB and SG) during the 24-h period after completion of the intervention.
- 9. Difference in %time in interstitial glucose levels <3.3 mmol/l in CGM between the two interventions (AEX vs control) after bariatric surgery (RYGB and SG) during the 24-h period after completion of the intervention.
- 10. Difference in % time in interstitial glucose levels <2.2 mmol/l in CGM between the two interventions (AEX vs control) after bariatric surgery (RYGB and SG) during the 24-h period after completion of the intervention.

- 11. Difference in % time in range (definition 1, defined as interstitial glucose levels between 3.9 7.8 mmol/l) in CGM between the two interventions (AEX vs control) after bariatric surgery (RYGB and SG) during the 24-h period after completion of the intervention.

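### Section 11.1 removes everyone whose meal test is stopped for symptomatic hypoglycaemia from all MMTT outcomes: this selects on the nadir being compared and, read literally, empties outcome 7

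*Protocol*

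**What the plan says.** Section 11.1 sets the rule. It opens with "In instances of symptomatic hypoglycaemia during the MMTT(where blood collection for glucose, insulin and appetite biomarkers" and the VAS scores being ended early, and concludes that "these participants will be excluded from the analysis of secondary outcomes related to the MMTT". It is the participant who is excluded, not only the samples after the stop, and no outcome is exempted.

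Sections 7.5 and 9.4 define the trigger: symptoms together with a low bedside capillary or venous reading at the 3.0 mmol/l threshold. Treatment follows and sampling ends.

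Section 5.2 lists the outcomes concerned:
- Outcome 1 is glucose AUC with "pre-meal, peak and nadir glucose levels after mixed meal tolerance test (3-h MMTT) between the two interventions". Outcome 2 is the insulin counterpart.
- Outcomes 3 to 6 are insulin/glucose AUC ratios (0-180, 0-30 and 60-180 min) and the maximum/minimum glucose ratio.
- Outcome 7 is "Difference at the number of mixed meal tests required to be stopped due to symptomatic HYPO", counted during the 3-h MMTT.
- Outcome 25 is the AUC of the hunger and satiety scores.

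Missing values are imputed only "within a completed MMTT will be imputed using a linear regression method as previously reported". Section 11.1 adds two sensitivity analyses. One removes participants who needed rescue in the 24 h after the intervention. The other admits participants with short CGM records.

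**The concern.** Whether a participant is analysed depends on what happened after randomisation, and the event is itself low glucose. The research hypothesis in section 3 is that exercise increases hypoglycaemia, so stops are expected to be commoner in the exercise condition. The people whose glucose fell furthest with symptoms would then leave both conditions, and the nadir comparison would rest on those who tolerated the test. In a study asking whether exercise does harm, that error points the wrong way.

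Two further costs need no assumption about direction. Data that were fully observed are discarded in a crossover of only 18 people. And the one outcome that counts stopped tests belongs to the family from which stopped tests are removed.

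**Working it through.** **1. The plan's own figure.** The protocol gives no figure for this exclusion. The nearest is the sample size in section 11.2, which fixes how many pairs there are to lose.
- SD of the paired difference = 25 × √(2 × (1 − 0.6)) = 22.36 min; target difference 18 min.
- Normal approximation: (22.36 × (1.960 + 0.842) / 18)² = 12.1, so 13; 13 / 0.8 gives 17.
- Noncentral t: n = 15 (power 0.826; n = 14 gives 0.795); 15 / 0.8 gives 19, and 15 × 1.2 = 18.

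The stated 18 is reproduced to within rounding and the choice of method. After 20% drop-out, 18 × 0.8 = 14.4 remain.

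**2. Outcome 7 under the literal rule.** Remove every participant with a stopped test in either period. The stops left in the analysed set are 0 in each condition, whatever the true rate.

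**3. What is discarded although it was measured.** Samples are taken pre-meal and at 15, 30, 60, 90, 120, 150 and 180 min. Section 3 places these episodes 1-3 h after a meal. By then the pre-meal values and the 0-30 min window are normally complete, and often the peak has been seen. All of this goes, along with the whole of the other period's test.

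**4. Pairs left.** The per-visit stop probability p is assumed. Pairs left from 18 are 18(1 − p)² if the periods are independent, and 18(1 − p) if the same people stop twice.

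| p | independent | same people |
|---|---|---|
| 5% | 16.2 | 17.1 |
| 10% | 14.6 | 16.2 |
| 20% | 11.5 | 14.4 |
| 30% | 8.8 | 12.6 |

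**5. Effect on the nadir difference (simulated; inputs assumed).** The only anchor in the documents is section 5.1, which expects 80% of episodes to be asymptomatic, hence 20% symptomatic. It is not specific to the meal test.

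*Set A.* Nadir SD 0.8 mmol/l, correlation 0.6, true exercise effect −0.40. A fixed share s of nadirs below 3.0 is symptomatic. The stop rate is s × Φ((3.0 − mean)/0.8). For example, with control mean 3.5 and s = 20%: control 0.2 × Φ(−0.625) = 0.053; exercise (mean 3.1) 0.2 × Φ(−0.125) = 0.090.

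| control mean | s | stops, control / exercise | excluded | difference after exclusion | mean exercise nadir, all → kept |
|---|---|---|---|---|---|
| 3.5 | 20% | 5.3% / 9.0% | 13.5% | −0.393 | 3.10 → 3.20 |
| 3.5 | 50% | 13.3% / 22.5% | 30.7% | −0.372 | 3.10 → 3.38 |
| 3.5 | 80% | 21.3% / 36.1% | 44.4% | −0.329 | 3.10 → 3.58 |
| 4.0 | 20% | 2.1% / 4.5% | 6.4% | −0.393 | 3.60 → 3.67 |
| 4.0 | 50% | 5.3% / 11.4% | 15.0% | −0.374 | 3.60 → 3.77 |
| 4.0 | 80% | 8.4% / 18.1% | 22.3% | −0.348 | 3.60 → 3.87 |

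At s = 20% the difference moves by about 0.01 mmol/l (0.007 / 0.40, about 2%). Of 18 participants, 18 × 0.064 = 1.2 to 18 × 0.135 = 2.4 are lost.

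*Set B.* Control mean 3.5, SD 0.6, correlation 0.6, effect −0.3, with symptoms likelier at deeper nadirs and the effect varying between people (SD 0 to 0.6). With 20% symptomatic, 9-11% are removed and the effect shrinks by 2-18%. Changing the steepness of the symptom curve gives 2-6% with a constant effect and 5-12% with effect SD 0.3. It can exceed 18% with effect SD 0.6, twice the mean effect. With 30-40% symptomatic, 16-22% are removed and shrinkage is 8-47%; the top of that range again needs effect SD 0.6.

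**The case against.** **Outcome 7 was surely not meant.** The exclusion sentence sits in a paragraph on computing AUC from blood samples, and a count of stops needs no samples. That is probably the intent. But the text makes no exception and outcome 7 is an MMTT outcome, so a clarifying line is still needed.

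**The main result is safe.** This stands. The 24-h CGM window starts when the intervention ends and so covers lunch. Participants who needed rescue stay in the main CGM analysis and leave only in a sensitivity analysis. CGM time below thresholds, LBGI and treated episodes still capture them. People with asymptomatic hypoglycaemia also stay in the MMTT analysis.

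**A stopped test cannot yield AUC(0-180).** True, and a reason to label truncated windows. It is no reason to delete pre-meal values, AUC(0-30) or the other period.

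Two stronger readings are tempting and are not supported:
- A reader might infer that the exclusion contradicts the rule that missing samples are imputed "provided baseline/pre meal value and ≥50% of data points within the MMTT are available", because a test stopped after the 120-min sample has 6 of 8 points (75%). The imputation covers completed tests only, and a stopped test is not completed, so the two rules do not conflict.
- A reader might infer that the whole of secondary objective 3, which begins "To assess the change in the nadir, peak and postprandial blood glucose levels", is biased towards no effect. Only the nadir was examined. Nothing in the documents fixes a direction for peak glucose, AUC or insulin.

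**Conclusion.** The rule is wrongly specified and should be changed; should-fix. Three parts follow from the text alone. Inclusion in the nadir comparison depends on a post-randomisation low-glucose event. Observed data from both periods are discarded. Sections 5.2 and 11.1 cannot both be followed literally for outcome 7. Neither sensitivity analysis brings these participants back into the MMTT outcomes.

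The bias on the nadir difference is probably towards no effect, provided exercise does cause more stops. Its size cannot be derived from the protocol, which gives no nadir mean, SD, effect or stop rate. At the expected 20% symptomatic share the attenuation is small in most of the scenarios tried. Large values need a higher symptomatic share or an exercise effect that differs widely between people. The loss of pairs and the upward shift in mean nadir (0.07 to 0.48 mmol/l in set A) are the more visible consequences.

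**What to change.** Amend section 11.1, before any results are seen, as follows.

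1. Count outcome 7 in everyone who started the MMTT, and say so in section 5.2.
2. In the main analysis keep participants with a stopped test, using every laboratory sample taken up to the stop and all data from their other period. GEE accepts incomplete pairs. State that the complete-case wording does not override this for the MMTT outcomes.
3. Take nadir and peak from the laboratory samples observed up to the stop. Use the bedside reading that triggered treatment only in a labelled sensitivity analysis: section 9.4 distinguishes it from laboratory plasma glucose, and it would enter stopped tests only.
4. Report time-averaged AUC over the same window in both periods for an affected participant, labelled as truncated. This is the matched-time principle that section 11.1 already applies to missing CGM data. Leave windows that were not reached, such as 60-180 min after an early stop, as missing.
5. Keep the present exclusion as a sensitivity analysis.

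The cost is wording; no new data are needed and hypoglycaemia management is unchanged. The downsides are a shorter AUC window for a few pairs and a laboratory nadir that may miss the lowest point when it falls between samples, which is why step 3 adds the bedside analysis. Participants with symptomatic hypoglycaemia between the intervention and lunch cannot be recovered for that period, because section 5.1 has their meal test go unsampled.

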#### 11.2 The Number of Participants

This is a proof-of-concept study and there are no previous data available on the acute effect of AEX on time spent on HYPO after bariatric surgery. Previous studies have found that people without diabetes after bariatric surgery spend on average 71±25 min/day in HYPO postoperatively (37) and that the incidence may be similar between RYGB and SG (13). Based on this previous research, the current we estimate that the research project is powered (80%) to detect a 25% difference (18 minutes/day) in time spent in HYPO during the first 24-hs between the AEX and control interventions, with 2-sided alpha set at 5% and assuming a standard deviation of 25min and a moderate within-person correlation of 0.6. On this basis, 18 participants are required for this crossover study (accounting for an estimated drop-out of 20%).

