#### 11.3 The Level of Statistical Significance

The results of all comparative analyses will be presented with 95% confidence intervals and statistical significance for main effects will be assessed at the 5% level. All p-values shown will be two-sided.

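### Section 11.1 plans GEE on about 14–18 participants with no small-sample correction stated; run in its usual form, the nominal 5% test has a size of about 7–8%

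*Protocol*

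**What the plan says.** Section 11.1 of the protocol states that the primary and secondary outcomes will be "analysed using GEE (Generalised Estimating Equations) with an exchangeable correlation matrix, taking into account repeated measures across conditions". It adds: "Outcome distribution will be assessed, with Gamma models used for positively skewed data", with an identity link preferred and a log link possible. The primary and main secondary analyses are complete-case.

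The error rate is fixed in two places. Section 11.1: "A value of P<0.05 will be considered statistically significant for all analyses". Section 11.3: "All p-values shown will be two-sided" and "The results of all comparative analyses will be presented with 95% confidence intervals".

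Section 11.2 says that "the research project is powered (80%) to detect a 25% difference (18 minutes/day) in time spent in HYPO", assuming an SD of 25 min and a within-person correlation of 0.6. It arrives at 18 participants, including 20% drop-out.

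The protocol names no variance estimator, small-sample correction or reference distribution, and leaves the software open. Section 11.5 refers to a statistical analysis plan, which is not at hand.

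**The concern.** GEE Wald inference is justified as the number of independent clusters grows. Here the clusters are participants, and there will be 18 at most. In its usual form the method divides the sum of squares by n where n-1 is needed, and it compares the statistic with 1.96 where a t quantile is needed. Both shortcuts push towards false positives and short intervals, and at this size neither is negligible.

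The primary comparison is affected along with the secondary ones. Section 3 says that if exercise increases time in hypoglycaemia, guidance on prevention and management may be needed. A positive result could therefore have consequences, and the test behind it should hold the level the protocol states.

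**Working it through.** **Inputs.** From section 11.2: difference 18 min/day, SD 25 min, correlation 0.6, two-sided alpha 5%, power 80%, 18 randomised, 20% drop-out. From section 11.1: exchangeable GEE, complete cases. Assumed, because the protocol does not say: uncorrected sandwich variance and normal reference.

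**1. The planned number reproduces.** The SD of the within-person difference is 25 × sqrt(2 × 0.4) = 22.36 min.
- Normal formula: (22.36 × (1.960 + 0.842) / 18)² = 12.1, so 13 pairs; 13/0.8 = 16.25, so 17.
- Paired t: 14 pairs give 79.5% power and 15 give 82.6%; 14/0.8 = 17.5, so 18.

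The stated 18 is not in dispute. The analysed number is about 18 × 0.8 = 14.4, so n = 14 to 18 covers the plausible range.

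**2. What the usual GEE test is here.** With a treatment term only, an identity link and two observations per person, the estimate is the mean paired difference. Let SS be the sum of squared deviations of the differences. The uncorrected sandwich variance is SS/n²; the paired t variance is SS/(n(n-1)). So z = t × sqrt(n/(n-1)). Under normality the size of the nominal 5% test is exactly

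P(|t on n-1 df| > 1.96 × sqrt((n-1)/n)).

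- n=14: threshold 1.96 × 0.9636 = 1.889, size **8.1%**.
- n=15: threshold 1.894, size 7.9%.
- n=18: threshold 1.96 × 0.9718 = 1.905, size **7.4%**.

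**3. Variants.**

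| Model and variance, normal reference | n=14 | n=18 |
|---|---|---|
| Treatment only, uncorrected | 8.1% | 7.4% |
| Treatment only, n/(n-1) factor | 7.2% | 6.7% |
| With period term, uncorrected | 9.5% | 8.3% |
| With period term, n/(n-1) factor | 8.4% | 7.5% |

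The period rows assume balanced sequences and use P(|t on n-2 df| > 1.96 × sqrt((n-2)/n)), or sqrt((n-2)/(n-1)) with the factor. Section 11.1 does not state a period term; the rows show what happens if one is added.

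**4. Interval width.** The correct t interval relative to the uncorrected GEE interval:
- Treatment only: 2.160/1.889 = 1.14 at n=14; 2.110/1.905 = 1.11 at n=18.
- With a period term: 2.179/1.815 = 1.20 at n=14; 2.120/1.848 = 1.15 at n=18.

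**5. Simulation check.** Exchangeable GEE, 1,500 runs per setting, mean 71, SD 25, correlation 0.6, sandwich standard error with z. The Monte Carlo margin is roughly ±1.2 to 1.5 percentage points.
- Normal data: 7.7% (n=14) and 6.4% (n=18) without a period term; 10.2% and 8.5% with one.
- Gamma data, with and without period: 7.5–9.8% with an identity link, 6.7–10.3% with a log link.
- Strongly skewed data (Gamma shape 1, an assumption that is not in the protocol), log link: 10.0–14.4%.
- Model-based standard errors with z, excluding the shape-1 case: 7.4–15.4%, so no better.

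**6. What a correction does in the treatment-only case.** Each participant has leverage 1/n. Kauermann–Carroll therefore gives variance SS/(n(n-1)); with t on n-1 df this is the paired t-test, size 5.0%. Mancl–DeRouen gives SS/(n-1)²; with t, size is P(|t on n-1 df| > t critical × sqrt(n/(n-1))), which is 4.3% at n=14 and 4.4% at n=18. Mancl–DeRouen with 1.96 in place of t still has 6.3% and 6.0%, so the t reference matters.

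**The case against.** The strongest reply is that the error is not in the text. Section 11.1 fixes GEE, a working correlation and a Gamma option. It does not say uncorrected sandwich, and it does not say 1.96. A 5% test and a 95% interval can both be delivered by GEE with a small-sample correction. The variance estimator is commonly left to a statistical analysis plan, and one may exist.

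Much of this stands. It makes the result conditional, and a plan that already specifies a corrected variance with a t reference would largely remove the problem. It does not dispose of the point. The protocol itself has put together the method, the error level and the sample size, and the named method in its ordinary form misses that level at that size.

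It can also be said that the study is labelled proof of concept and the inflation is moderate. Both are true. Section 11.2 still makes a formal claim of 80% power at a two-sided 5% level.

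A reader might infer more: that the trial's true error rate is simply 7–9%, that every p-value and interval is wrong by these amounts, or that GEE and the Gamma models must be abandoned. The documents do not support this. The estimator is not named. The exact results cover only normal data with an identity link. The listed outcomes include event counts and stopped meal tests, for which no exact figure was derived. Replacing the Gamma option throughout would go beyond the defect.

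**Conclusion.** The point holds in conditional form and should be fixed. If the GEE of section 11.1 is run with the usual sandwich standard error and a normal reference on 14 to 18 participants, the nominal two-sided 5% test has a size of about 7–8% in the treatment-only identity-link model. Across the variants in the table the range is 6.7–9.5%, about 1.3 to 1.9 times the stated level. P-values would be too small, and the intervals would need to be 11–14% wider, or 15–20% with a period term.

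This rests on three assumptions: normal data, default GEE inference, and no correction in an unseen analysis plan. Simulation suggests that moderately skewed Gamma models behave similarly and strongly skewed data worse, but those results depend on the distribution assumed. The treatment-only identity-link point estimate is unaffected, and so is the sample size calculation.

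**What to change.** Add to section 11.1 that GEE inference will use a small-sample bias-corrected sandwich variance (for example Kauermann–Carroll or Mancl–DeRouen) with t critical values based on the number of participants: n-1 degrees of freedom for a treatment-only model, n-2 with a period term. For continuous identity-link outcomes, including the primary, the equivalent paired or period-adjusted t analysis may be named instead. Keep the Gamma option for skewed outcomes, with the same correction. If the statistical analysis plan already says this, a cross-reference is enough.

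The cost is one sentence and wider intervals, by the percentages above. No participants or visits are added: on the protocol's own inputs a paired t analysis has 79.5% power with 14 pairs and 89.6% with 18. One limit remains. Under the assumed shape-1 skew, a bias-reduced sandwich with z still simulated at 8.1–10.3%. The t reference would lower this but was not simulated there, so Gamma results from very skewed outcomes should be read with caution even after the correction.
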